3.3.4. Baseline

Baseline for clinical laboratory results and VS will be defined as the last result obtained before study product administration. If triplicate ECG measures were performed at the same visit, baseline ECG will be defined as the mean value of the last triplicate measurements before study product administration.

Baseline height, weight, and body mass index (BMI) will be the measurements obtained at Screening. Age will be based on age at the time of enrollment.

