4. INVESTIGATIONAL PLAN

4.1. Overall Study Design and Plan

This is a Phase 1, randomized, double-blind, placebo-controlled, SAD study in healthy adult subjects. It is designed to evaluate the safety and PK of single oral doses of VT-1598. An overall schematic of study design is shown in [Figure 1](#). A flowchart of subject disposition will be shown in [Figure 2](#), and a table showing all planned study cohorts and dose levels can be found in [Table 1](#). There will be 5 fasted cohorts: 40 mg VT-1598 or matching placebo, 80 mg VT-1598 or matching placebo, 160 mg VT-1598 or matching placebo, 320 mg VT-1598 or matching placebo, 640 mg VT-1598 or matching placebo, and one fed cohort: 160 mg VT-1598 or matching placebo following a high-fat, high-calorie meal.

A maximum of 40 subjects at a single site will be enrolled in the study to one of the fasted cohorts (Cohorts 1-5). Within each fasted cohort, a total of 8 subjects will be randomized 3:1 to receive active drug (VT-1598) (6 subjects) or placebo (2 subjects). For Cohort 1 through Cohort 5, the first 2 subjects will be randomized 1:1 to receive active drug or placebo to ensure that 1 of the first 2 subjects receives active drug and the other receives placebo for sentinel dosing. The study product assignment of the remaining 6 subjects in each of the fasted cohorts (Cohorts 1-5) will be randomly assigned 5:1 active drug to placebo to maintain the 3:1 ratio for the entire cohort. All sentinel subject safety data through Day 3 will be reviewed by the Principal Investigator (PI) prior to dosing the remaining 6 subjects in each fasted cohort.

Subjects who complete Cohort 3 and do not early terminate from the study will have enrollment “rollover” to Cohort 6, the fed cohort, after a minimum of 60 days for a “wash-out” period. Cohort 3 subjects continuing to Cohort 6 will not be randomized but will receive the same study product and dose as they received in Cohort 3 (160 mg VT-1598 or matching placebo) following a high-fat, high-calorie meal. Furthermore, there will be no sentinel subjects in Cohort 6. Cohort 3 subjects that are no longer eligible for the trial after the wash-out period will be replaced ([Section 4.4.3](#)). Subjects replacing individuals from Cohort 3 who did not continue on to Cohort 6 will not be randomized and will receive the same study product assignment as the Cohort 3 subject they are replacing.

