6. GENERAL STATISTICAL CONSIDERATIONS

6.1. General Principles

Summary statistics for continuous data will include the number of subjects included in analysis (N), mean, standard deviation (SD), median, minimum value (min), and maximum value (max). Summary statistics for discrete data will include frequencies and proportions and may include confidence intervals (CIs) for the proportion. When 95% CIs are given for a proportion, exact (Clopper-Pearson) CIs will be used, unless otherwise specified. All randomized subjects will be included in the summaries of subject demographics. The Safety Population will be used for summaries of safety endpoints and the PK Analysis Population or the PK Analysis Subset will be used for summaries of PK endpoints.

Denominators for safety endpoints will be the number of subjects in the Safety Population. Denominators for clinical laboratory, VS, and ECG results at planned study timepoints will be the number of subjects with available results at the specified timepoint for that parameter. Denominators for the conceptual “Maximum Severity Post Baseline” timepoint for clinical laboratory, VS, and ECG results will be the number of subjects with an observed result for the parameter obtained post dose.

The sort order for listings is indicated in the implementation note for each listing shell ([Appendix 3](#)). The sort order of clinical laboratory tests, VS, and ECG parameters is described in Section [9](#).

All safety and PK analyses will be performed by Dose Group as described in Section [3.3.2](#).

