9.1. Demographic and Other Baseline Characteristics

Sex, ethnicity, and race of all subjects will be summarized by Dose Group ([Table 12](#)). Ethnicity will be categorized “Hispanic or Latino,” or “Not Hispanic or Latino,” “Unknown,” or “Not Reported.” In accordance with National Institutes of Health (NIH) reporting policies, subjects may self-designate as belonging to more than one race or may refuse to identify a race, the latter reflected in the case report form (CRF) as “No” to each race option. Age at enrollment, height, weight and BMI at Screening will be summarized by Dose Group ([Table 13](#)). Individual subject listings will be presented for all demographic and baseline characteristics ([Listing 6](#)).

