10.3.1. Assessment of Dose Proportionality

The presence of dose proportionality in plasma in terms of exposure parameters (C_{max}, AUC_{0-last}, and AUC_{0-inf}) over the range of studied doses will be assessed among the Fasted Dose Groups using a power model approach with methods described by Smith et al. [5] The PK Analysis Subset will be used for this analysis.

The power model for the specific case of AUC_{0-last} may be specified with model parameters α and β to be estimated as:

$$AUC_{0-last} = e^\alpha \times dose^\beta$$

Let ρ be the highest dose studied / lowest dose studied and let (L, U) represent the 90% CI for β . In the presence of dose proportionality, $\rho^{\hat{\beta}}/\rho = \rho^{\hat{\beta}-1} = 1$. Note that normality of $\hat{\beta}$ is assumed, and this assumption implies that $\rho^{\hat{\beta}-1}$ has an assumed log-normal distribution. Accordingly, dose proportionality across the studied dose range is concluded using methodology analogous to that commonly used for an assessment of bioequivalence when:

$$\Theta_1 = 0.8 \leq \rho^{L-1} < \rho^{U-1} \leq 1.25 = \Theta_h.$$

Or, equivalently,

$$1 + \frac{\log 0.8}{\log \rho} \leq L < U \leq 1 + \frac{\log 1.25}{\log \rho}.$$

The analysis may be inconclusive if the CI (ρ^{L-1}, ρ^{U-1}) overlaps partially with the interval (0.80, 1.25) or if the (ρ^{L-1}, ρ^{U-1}) contains the interval (0.80, 1.25).

If graphical evidence suggests dose proportionality may exist over a subset of the dose range, the above criteria of Smith et al [5]. may be applied to a subset of the data only containing values for subjects within a limited dose range. If lack of dose proportionality is evident for higher doses, other dose proportionality analyses using a subset of the full dose range studied may be explored.

Dose proportionality assessments will be presented graphically and tabularly:

- Tabular results of statistics and parameters from the plasma dose proportionality power model will be presented for both VT-1598 and VT-11134 in [Table 101](#).
- Predicted values from a power model, including 90% pointwise prediction bands, will be overlaid on plots of the exposure parameter parameters (C_{max}, AUC_{0-last}, or AUC_{0-inf}) versus dose. Pointwise prediction bands will be defined by lower and upper limits of 90% pointwise prediction intervals

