10.3.3. Analysis of Exposure Parameter Ratios between Fasted and Fed Dose Groups

Exposure parameters (C_{max} , AUC_{0-last} , and AUC_{0-inf}), will be compared between the 160 mg Fasted and Fed Dose Groups using the PK Analysis Subset. The ratio of the GM of each parameter for the fed group compared to the GM of the same parameter in the corresponding fasted group will be estimated using a mixed effects model. Each exposure parameter will be estimated by fasting status with a random subject effect and a heterogeneous compound symmetry covariance structure. Because a random subject effect will be included, only one analysis will be conducted on all subjects in the 160 mg Fasted and 160 mg Fed Dose Groups for each exposure parameter, regardless of whether the subject participated in both dosing periods. In the event of nonconvergence of the model, first an unstructured covariance matrix will be specified. If the model still fails to converge the random subject effect will be removed from the model.

[Table 103](#) will display results comparing exposure parameters in both VT-1598 and VT-11134 between the 160 mg Fasted and 160 mg Fed Dose Groups, including the ratio estimate and a 90% CI.

Pseudo code to estimate the ratio of exposure parameters between the 160 mg Fasted and 160 mg Fed Dose Groups is presented below. Variables to be used in the model are also detailed below:

- FedCondition = indicator for dose received and fasting status; 160 mg Fed = 1, 160 mg Fasted = 2
- ExposureParam_LN = log transformed values of exposure parameters for each subject.

```
proc mixed data=data;
  class Subject_ID FedCondition;
  model ExposureParam_LN= Subject_ID FedCondition /DDFM=SATTERTH;
  random FedCondition /type=CSH sub= Subject_ID G;
  repeated /grp= FedCondition sub= Subject_ID;
  estimate 'Ratio of Fed to Fast' FedCondition 1 -1/CL alpha=0.1;
run;
```

Where `ExposureParam_LN` is the natural log of the exposure parameter being modeled (C_{max} , AUC_{0-last} , and AUC_{0-inf}) and `FedCondition` is a variable indicating the fed vs fasting condition. The `estimate` statement will give the mean of the natural log values of each exposure parameter and the associated 90% CIs on the log scale. Exponentiating the results of the `estimate` statement will give the GM and associated 90% CIs for each exposure parameter.

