15. SUMMARY OF CHANGES IN THE CONDUCT OF THE STUDY OR PLANNED ANALYSES

Only one subject from the fasted 160 mg cohort (Cohort 3) returned for the fed 160 mg cohort (Cohort 6). This impacts the planned analysis of change in T_{max} between fasted and fed Dose Groups. Previously, an exact Wilcoxon-signed rank test had been proposed to compare subjects who had participated in both cohorts, however since fewer than 3 subjects were present in both cohorts, this analysis was not completed. Instead, only an exact Wilcoxon rank sum test was performed to compare the change in T_{max} between fasted and fed Dose Groups.

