9.5.1 Pharmacokinetics and Safety Measurements Assessed and Flow Chart

Table 2: Schedule of Study Procedures

Activity	Screening	Baseline	Inpatient (Treatment) Period			Follow-up Period			Unscheduled
Study Visit	Visit 1	Visit 2	Visit 3			Visit 4	Visit 5	Visit 6	
Study Day	Day -28 to -2	Day -1	Day 1	Days 2 & 3	Day 4	Day 7 (± 1 day)	Day 14 (± 1 day)	Day 21/ End of Study ^s (± 2 days)	
Informed Consent	X								
Demographics	X								
Inclusion/Exclusion Criteria	X	X							
Height, Weight, BMI	X	X ^a							
Medical History ^b	X	X ^c				X ^c	X ^c	X ^c	
Physical Examination	X ^d	X ^e	X ^e		X ^e			X ^e	X ^e
Vital Signs ^f	X ^f	X ^f	X ^f	X ^f	X ^f	X ^f	X ^f	X ^f	X ^f
ECG ^g	X ^g		X ^g		X ^g			X ^g	X ^g
Clinical Laboratory Tests ^h	X	X			X	X	X	X	X
Pregnancy Test ⁱ	X	X						X	
FSH ^j	X								
Drug Screen ^k	X	X							
Immunology Screen ^l	X								
PK Blood Samples ^m			X ^m	X ^m	X ^m	X ^m	X ^m	X ^m	X ^m
PK Urine Samples ⁿ			X ⁿ	X ⁿ	X ⁿ				
Future Use Specimen Collection			X						
Prior/Concomitant Medications/Treatments	X	X	X ^o	X	X	X	X	X	X

Activity	Screening	Baseline	Inpatient (Treatment) Period			Follow-up Period			Unscheduled
Study Visit	Visit 1	Visit 2	Visit 3			Visit 4	Visit 5	Visit 6	
Study Day	Day -28 to -2	Day -1	Day 1	Days 2 & 3	Day 4	Day 7 (± 1 day)	Day 14 (± 1 day)	Day 21/ End of Study ^s (± 2 days)	
Review/confirm adherence to dietary restrictions/birth control methods ^p	X	X			X	X	X	X	
Admit to CRU		X							
Discharge from CRU					X				
Receive study product ^{q,r}			X						
Collect and Record AEs			X	X	X	X	X	X	X

*Cohort 6 may enroll prior to the SMC meeting or prior to the start of Cohort 5 (but no less than 60 days after completion of Cohort 3).

Abbreviations: AE: adverse event; BMI: body mass index; ECG: electrocardiogram; EW: early withdrawal; FSH: follicle-stimulating hormone; HIV-1: Human Immunodeficiency Virus-1; HIV-2: Human Immunodeficiency Virus-2; HBsAg: Hepatitis B surface antigen; Anti-HCV: anti-Hepatitis C virus; IMP: investigational medicinal product; PK, pharmacokinetics.

^a Weight and BMI only.

^b Including alcohol and tobacco use history.

^c Update medical history as appropriate from previous visit.

^d Complete physical examination (general appearance; head, eyes, ears, nose, and throat; neck; chest and lungs; cardiovascular system, abdomen, musculoskeletal system, lymph nodes, extremities/skin, and neurological system).

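### Body weight is recorded twice before dosing but enters neither exposure model; a pre-specified weight-adjusted sensitivity analysis would recover precision and guard against a systematic weight shift between cohorts

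*SAP*

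**What the plan says.** **Weight.** SAP 3.3.4 fixes the baseline value: "Baseline height, weight, and body mass index (BMI) will be the measurements obtained at Screening". The schedule (SAP Table 2) repeats the measurement on Day -1, with the footnote "Weight and BMI only". The planned use is descriptive. SAP 9.1 says "Age at enrollment, height, weight and BMI at Screening will be summarized by Dose Group" (Table 13), and individual values go to Listings 6 and 19. SAP 6.4 names no covariate.

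**Dose proportionality.** In SAP 10.3.1, proportionality "over the range of studied doses will be assessed among the Fasted Dose Groups using a power model approach". Dose is the only predictor. The 90% CI for rho^(beta-1) is compared with 0.80-1.25, and Table 101 prints a Yes/No answer.

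**Food effect.** In SAP 10.3.3, "Each exposure parameter will be estimated by fasting status with a random subject effect". The 90% CI for the ratio is again compared with 80-125%. There is no weight term.

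**Allocation.** Protocol 10.3.1 randomises active against placebo within each fasted cohort, never between dose levels, and does not randomise Cohort 6. SAP 4.1 adds: "Subjects replacing individuals from Cohort 3 who did not continue on to Cohort 6 will not be randomized". SAP 15 reports: "Only one subject from the fasted 160 mg cohort (Cohort 3) returned for the fed 160 mg cohort (Cohort 6". It does not say which treatment that subject received.

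**Demographics.** SAP 6.1 says "All randomized subjects will be included in the summaries of subject demographics". SAP 9.1 covers all subjects by Dose Group. The shells of Tables 12 and 13 have a 160 mg Fed column, with N defined as enrolled/randomized.

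**The concern.** A fixed mg dose usually gives lower exposure in a heavier person, and eligibility allows a wide range: at least 50 kg, with BMI up to 35 (at an illustrative height of 1.90 m, 35 x 1.90^2 = 126 kg). With six active subjects per group, mean weight will differ between groups. If weight affects exposure, it adds variance that a recorded baseline value could remove. Both analyses give a verdict based on a CI, so residual variance affects the answer.

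Randomisation protects neither comparison from a weight trend. Dose levels are enrolled one after another. The food-effect comparison was planned within subject but became almost wholly between subjects when only one Cohort 3 subject returned. SAP 15 adapts the Tmax analysis to this and does not mention the exposure ratio.

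**Working it through.** The plan states no power calculation, CV or weight SD, so there is no figure to reproduce.

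**Inputs from the documents:** five fasted doses from 40 to 640 mg, each double the last, with 6 active subjects each; rho = 640/40 = 16; 90% CIs; limits 0.80-1.25.

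**Assumptions (not in the documents):** SD of ln(weight) 0.18 (range 0.15-0.20); exposure proportional to weight^-e with e = 0.75 (range 0-1); total CV of exposure 20-50%, with total variance ln(1+CV^2) held fixed.

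**1. Dose slope, chance imbalance**
- Tolerance on beta: ln(1.25)/ln(16) = 0.0805.
- Sxx of ln(dose) = 6 x (4+1+0+1+4) x (ln 2)^2 = 28.83, with square root 5.369.
- SD of beta due to weight = 0.18 x 0.75/5.369 = 0.025, or 31% of the tolerance. At e = 1 it is 0.0335, or 42%. Over SD 0.15-0.20 and e 0.5-1.0 it is 0.014-0.037.
- This scatter is already part of the residual. Simulated coverage of the unadjusted 90% CI is 0.896-0.903.

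**2. Gain from adding ln(weight)** (simulation, e = 0.75, truly proportional drug). The weight share of variance is (0.18 x 0.75)^2 = 0.0182 divided by ln(1+CV^2).

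| CV | Weight share | Chance of concluding proportionality, dose only | With ln(weight) |
|---|---|---|---|
| 20% | 46% | 38% | 76% |
| 25% | 30% | 11% | 29% |
| 30% | 21% | about 2% | about 5% |
| 40% | 12% | about 0 | about 0 |

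The mean CI width for beta falls from 0.124 to 0.093 at CV 20%, from 0.184 to 0.167 at 30%, and from 0.242 to 0.231 at 40%. With e = 0.5 the gains are smaller: 38% to 52% at CV 20%, and 10% to 15% at CV 25%. With e = 0 the CI is about 2% wider, and 38% becomes 35% at CV 20%.

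**3. Dose slope, systematic shift.** Suppose mean weight rises 3% per dose doubling. The bias in beta is about -0.75 x 0.03/ln 2 = -0.032. At CV 30%, unadjusted coverage falls to 0.84; adjusted coverage is 0.895.

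**4. Fed/fasted ratio** (treated as unpaired 6 v 6, which approximates the random-subject text)
- SD of the log ratio due to weight = 0.18 x 0.75 x sqrt(2/6) = 0.078, about 8% on the ratio.
- Log-scale CI width, unadjusted to adjusted: 0.406 to 0.317 (CV 20%), 0.601 to 0.571 (30%), 0.789 to 0.786 (40%), 0.960 to 0.980 (50%). With e = 0 it is about 7% wider.
- If the fed group is 10% heavier, the bias is about -0.75 x ln(1.1) = -0.07. At CV 30%, coverage is 0.87 unadjusted and 0.90 adjusted.

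**5. The printed code in SAP 10.3.3.** It lists Subject_ID in the MODEL statement, which makes subject a fixed effect. A rank check on 12 active-dose observations shows the result:
- If the returning subject was on VT-1598 (11 subjects), the fed effect is that subject's own difference. All other observations have weight 0, and there are 0 residual df.
- If the returning subject was on placebo (12 subjects), the fed effect is not estimable.

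In either case, between-subject weight cannot enter the ratio. Step 4 applies only to the model that the text describes.

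**The case against.** **Chance imbalance is already allowed for.** A reader might infer that an unlucky weight distribution would make a proportional drug look non-proportional, or create a food effect, more often than the CI admits. The documents do not support that: the scatter is in the residual, coverage stays near 90%, and SAP 10.3.1 allows an inconclusive result. This objection stands. The chance mechanism costs precision only. Bias needs a systematic cohort difference, which sequential enrolment permits but nothing in the documents shows.

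**The size rests on assumptions.** The gain is large only when weight explains a large share of variance (46% in the most favourable row of the table), and it nearly disappears by CV 30%. The protocol's animal data (Section 2.1) show less than proportional exposure, so the proportional-drug scenario may not apply. This stands too.

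**The analyses are exploratory.** Protocol 10.1 tests no formal hypotheses, and the fed/fasted comparison is labelled exploratory. SAP 15 is written partly in the past tense, so changing the main model now could look post hoc. This is a good reason to report adjustment beside the planned model, not in its place. It is no reason to leave the recorded weight unused.

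**The fed subjects are not left out of the demographics.** Read literally, SAP 6.1 excludes the non-randomised Cohort 6 replacements, and a reader might infer that Tables 12 and 13 hide the fed group. They do not: SAP 9.1, both table shells and Listing 6 cover these subjects. Only the sentence in 6.1 is out of line.

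**Conclusion.** The point holds as a matter of precision and robustness. The planned intervals remain valid under chance imbalance. Weight is available, is plausibly related to exposure at a fixed mg dose, and is absent from both models, while neither the dose comparison nor the fed/fasted comparison is protected by randomisation.

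Under the stated assumptions, adjustment about doubles the chance of a correct proportionality conclusion at CV 20%, helps at 25%, and adds little at 30% or above. It also removes the bias from a systematic weight shift, which the unadjusted CI does not cover. The weight SD, the exponent and the CV are all assumed, so the actual gain is unknown until the data are seen.

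For the food effect, the conflict between text and code in SAP 10.3.3 comes first, because the printed code discards every subject except at most one. The inconsistency in SAP 6.1 is a wording matter only.

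**What to change.** 1. **SAP 10.3.1:** pre-specify a second power model that adds ln(body weight), using the Day -1 value, or Screening if that is missing. Report its beta and 90% CI beside the planned dose-only result in Table 101. The 0.80-1.25 rule is unchanged.
2. **SAP 10.3.3:** decide whether subject is random (text) or fixed (code) and make the two agree. Then report a weight-adjusted fed/fasted ratio beside the planned one in Table 103.
3. **SAP 6.1:** change the demographic population to all enrolled subjects, in line with SAP 9.1 and Tables 12-13.
4. State in the SAP when the adjusted analyses were added relative to unblinding and database lock.

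**Cost:** wording, one model term and extra table rows, using data already collected, with no change to visits or procedures. Each adjusted model spends 1 df. If weight is irrelevant, its CI is about 2% wider in the 30-subject model and about 7% wider in the 12-subject comparison. At high CV the 12-subject CI can widen slightly even if weight matters. Keeping the planned results alongside contains that cost.

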3.3.5. Study Day

Study Day will primarily be used in listings to refer to the timing of assessments and events relative to study product administration. The day that the first dose of study product is received is considered Study Day 1 for all subjects. The day prior to the first dose is considered Study Day -1, there is no Study Day 0.

4. INVESTIGATIONAL PLAN

4.1. Overall Study Design and Plan

This is a Phase 1, randomized, double-blind, placebo-controlled, SAD study in healthy adult subjects. It is designed to evaluate the safety and PK of single oral doses of VT-1598. An overall schematic of study design is shown in [Figure 1](#). A flowchart of subject disposition will be shown in [Figure 2](#), and a table showing all planned study cohorts and dose levels can be found in [Table 1](#). There will be 5 fasted cohorts: 40 mg VT-1598 or matching placebo, 80 mg VT-1598 or matching placebo, 160 mg VT-1598 or matching placebo, 320 mg VT-1598 or matching placebo, 640 mg VT-1598 or matching placebo, and one fed cohort: 160 mg VT-1598 or matching placebo following a high-fat, high-calorie meal.

A maximum of 40 subjects at a single site will be enrolled in the study to one of the fasted cohorts (Cohorts 1-5). Within each fasted cohort, a total of 8 subjects will be randomized 3:1 to receive active drug (VT-1598) (6 subjects) or placebo (2 subjects). For Cohort 1 through Cohort 5, the first 2 subjects will be randomized 1:1 to receive active drug or placebo to ensure that 1 of the first 2 subjects receives active drug and the other receives placebo for sentinel dosing. The study product assignment of the remaining 6 subjects in each of the fasted cohorts (Cohorts 1-5) will be randomly assigned 5:1 active drug to placebo to maintain the 3:1 ratio for the entire cohort. All sentinel subject safety data through Day 3 will be reviewed by the Principal Investigator (PI) prior to dosing the remaining 6 subjects in each fasted cohort.

Subjects who complete Cohort 3 and do not early terminate from the study will have enrollment “rollover” to Cohort 6, the fed cohort, after a minimum of 60 days for a “wash-out” period. Cohort 3 subjects continuing to Cohort 6 will not be randomized but will receive the same study product and dose as they received in Cohort 3 (160 mg VT-1598 or matching placebo) following a high-fat, high-calorie meal. Furthermore, there will be no sentinel subjects in Cohort 6. Cohort 3 subjects that are no longer eligible for the trial after the wash-out period will be replaced ([Section 4.4.3](#)). Subjects replacing individuals from Cohort 3 who did not continue on to Cohort 6 will not be randomized and will receive the same study product assignment as the Cohort 3 subject they are replacing.

A schedule of study procedures is detailed in [Table 2](#). Screening, baseline, and follow-up procedures will follow the same process for all cohorts. Inpatient period (Study Days 1-4) procedures will differ between the fasted (Cohorts 1-5) and fed (Cohort 6) cohorts only by the high-fat, high-calorie meal and timing of inpatient pre-dose assessments. Baseline blood PK samples, targeted physical examination, and 12-lead ECG will be conducted within 60 minutes of dosing for the fasted cohorts (Cohorts 1-5). Baseline urine PK samples will be collected within 6 hours prior to dosing for the fasted cohorts (Cohorts 1-5). For Cohort 6, these procedures will be conducted within 30 minutes prior to the start of the meal. The high-fat, high-calorie meal will be entirely consumed within 30 minutes, and Cohort 6 subjects will be dosed within 30 minutes of the start of the meal. Post-dose inpatient period procedures will be the same for all cohorts. Safety assessments will include clinical laboratory tests including CHEM, HEM, COAG, and UA; VS; and a 12-lead standard ECG. AEs and serious adverse events (SAEs) will be assessed from the time of dosing to the end of the trial.

A Safety Monitoring Committee (SMC) will be appointed to oversee the safe conduct of the trial. If criteria for halting the trial are met during the study, dosing and enrollment will be suspended, and an *ad hoc* SMC meeting will be convened to review all available safety data and to make recommendations about the dosing of all further subjects in the trial. A scheduled SMC meeting will be held after Cohort 4 for safety recommendations and confirmation of dosing before beginning Cohort 5. The SMC will also review safety data at an organizational meeting prior to the start of the study, at a scheduled meeting upon completion of dosing, final visit for all cohorts, and at the request of DMID.

There will be an interim analysis of PK data after completion of Cohort 3. The interim PK report will show PK data in aggregate and will not include any potentially unblinding information. Enrollment will not stop for the interim PK analysis. If PK is substantially different than expected, the protocol may be amended to change the timing of PK samples.

